Conservative management of MNP includes medications and physiotherapy. Physiotherapy includes exercise (stretching, strengthening, stabilization, endurance training), manual therapy (muscle energy technique as post isometric relaxation, myofascial release, trigger point release), dry needling, ultrasound, laser, electrotherapy, heat or infrared and ice with weak evidence for their efficacy except for exercises (**Leaver et al., 2010; Desai et**

al., 2013; Gross et al., 2015; Cerezo-Tellez et al., 2016; Cohen and Hooten, 2017; Thomas et al., 2019; Sbardella et al., 2021; Samiullah et al., 2022).

Myofascial release therapy, deep friction massage, stretching, and/or isometric exercises can improve pain, function, cervical ROM, and/or Quality of life in patients with neck pain (Hou et al., 2002; Pesco et al., 2006; Salo et al., 2010; Blanpied et al., 2017; Khan et al., 2022).

Extracorporeal shockwave therapy has been shown to reduce neck pain, pressure pain threshold, and disability in patients with neck pain with trigger points. However, because the studies of neck pain are of low quality due to lack of blinding and small sample size so its efficacy remains unknown (Yoo et al., 2020; Jun et al., 2021).

Statement of the problem

This study will try to answer the following question what is/are the effect(s) of adding extracorporeal shockwave therapy to the Routine physiotherapy on pain, function, range of motion (ROM), and position sense in patients with chronic mechanical neck pain?

Purposes of the study

The purpose of this study to explore the effect the effect of adding extracorporeal shockwave therapy to the Routine physiotherapy on neck pain, function, ROM, joint position sense in patients with chronic mechanical neck pain.

Significance of the study

Mechanical neck pain is a frequent condition that has a detrimental impact on patient's biopsychosocial characteristics as a results of increased

muscle tension (**Heintz & Hegedus, 2008; Genebra et al., 2017; Osama & Rehman, 2020; Erdem et al., 2021**).

Physiotherapy interventions for MNP is effective in short-term, however they lack high quality evidence (**Desai et al., 2013; Cohen and Hooten, 2017; Sbardella et al., 2021; Samiullah et al., 2022**).

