Extracorporeal shockwave therapy for treatment of MNP is promising in increasing pressure pain threshold and decreasing disability. Although further high-quality studies were needed to confirm its efficacy (**Carroll et al., 2009; Cohen and Hooten, 2017; Manafnezhad et al., 2019**).

Myofascial syndrome, which is characterized by taut bands that cause pain and limit range of motion in individuals with non-specific neck pain, is a substantial source of pain, hence breaking the cycle of pain by relaxing tense bands is primary goal of its treatment (**Rahbar., 2021**).

The efficacy of Extracorporeal shock wave therapy on myofascial condition is now the subject of more research to determine its effectiveness, especially in the upper trapezius which need further research to confirm its pain-relieving characteristics and their capability to promote tissue proliferation and repair (**Rahbar., 2021**).

Consequently, extracorporeal shockwave therapy combined with Routine physiotherapy needs to be investigated whether it will be helpful in improving clinical outcomes of mechanical neck pain or not.

Several therapies were used to treat MNP patients; nonetheless, MNP is quite common, with most patients experiencing chronic and recurring symptoms after one year. Newer interventions as extracorporeal shockwave

therapy may help to treat this condition well (**Carroll et al., 2009; Cohen and Hooten, 2017; Manafnezhad et al., 2019**).

Hypotheses

It is hypothesized that:

- 1- There will be no significant effect of adding ESWT to routine physiotherapy on pressure pain threshold in patients with MNP.
- 2- There will be no significant effect of adding ESWT to routine physiotherapy program on neck function in patients with MNP.
- 3- There will be no significant effect of adding ESWT to routine physiotherapy on cervical flexion active range of motion (AROM) in patients with MNP.
- 4- There will be no significant effect of adding ESWT to routine physiotherapy on cervical extension AROM in patients with MNP.
- 5- There will be no significant effect of adding ESWT to routine physiotherapy on cervical side bending to the right AROM in patients with MNP.
- 6- There will be no significant effect of adding ESWT to routine physiotherapy on cervical side bending to the left AROM in patients with MNP.
- 7- There will be no significant effect of adding ESWT to routine physiotherapy on cervical rotation to the right AROM in patients with MNP.

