- 8- There will be no significant effect of adding ESWT to routine physiotherapy on cervical rotation to the left AROM in patients with MNP.
- 9- There will be no significant effect of adding ESWT to routine physiotherapy on cervical flexion joint position sense (JPS) in patients with MNP.
- 10-There will be no significant effect of adding ESWT to routine physiotherapy on cervical extension JPS in patients with MNP.
- 11-There will be no significant effect of adding ESWT to routine physiotherapy on cervical side bending to the right JPS in patients with MNP.
- 12-There will be no significant effect of adding ESWT to routine physiotherapy on cervical side bending to the left JPS in patients with MNP.
- 13-There will be no significant effect of adding ESWT to routine physiotherapy on cervical rotation to the right JPS in patients with MNP.
- 14-There will be no significant effect of adding ESWT to routine physiotherapy on cervical rotation to the left JPS in patients with MNP.

Delimitations

This study will be delimited to the following:

1. Fifty-two patients (males and females) with non-specific neck pain.
2. The age of the patients will range between 18-29 years (Jahre et al., 2020).

3. The instrumentations will be limited to: Pressure algometer to assess pressure pain threshold, The Arabic version of Neck disability index (NDI) to assess neck function, and goniometer to assess cervical range of motion (CROM) and joint position sense, at base line and after 4 weeks of treatment.
4. The intervention will be limited to; extracorporeal shockwave therapy and routine physiotherapy (Deep friction massage, stretching, isometric training, and home program of postural correction).

Basic Assumption

It will be assumed that:

1. All subjects will be committed to the therapist instructions and to assessment and treatment steps during the study.
2. All subjects will not take any medications or modality that interfere with the treatment in this study.

Definition of terms:

Joint position sense: is the ability of a person to perceive a presented joint angle and then, after the limb has been moved, to actively or passively reproduces the same joint angle. (**Riemann & Lephart, 2002**).

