Inclusion criteria

Patients will be included in the study if they fulfil the following criteria:

1. Patients (both males and females) with neck pain for more than three months.
2. Patients will be aged between 18 and 29 years old (**Jahre et al., 2020**).
3. Patient has at least one taut band at upper fibers of trapezius as described in assessment procedures.
4. Patient visual analogue scale (VAS) 3 to 8 out of 10

Exclusion criteria:

Patients will be excluded if they:

1. Were treated for neck or shoulder pain during the last three months.
2. Had neck or shoulder operation during the last two years.
3. Had any structural pathology of the cervical spine, such as disk prolapse, spinal stenosis, or cervical spondylosis.
4. Had traumatic history, instability, spasmodic torticollis.
5. Had cardiovascular, respiratory, or allergic disease, neck osteoarthritis.
6. Had homeostatic disorders.
7. Fibromyalgia, shoulder diseases (tendonitis, bursitis, capsulitis).
8. inflammatory rheumatic diseases.
9. Severe psychiatric illness and other diseases that restrict physical loading, and pregnancy (**Salo et al., 2010**).

Instrumentations:

A. Assessment tools:

1. Pressure algometer (with a circular flat tip of 1 cm² will be used to assess pressure pain threshold (**Asiri et al., 2020**). The reliability is excellent (**Walton et al., 2014**).
2. The Arabic version of Neck disability index (NDI) will be used to assess neck function. It includes questions regarding daily living activities such personal care, lifting, reading, working, driving, sleeping, and recreation activities as well as pain severity, focus, and headache (**Elbeltagy et al., 2020**).
3. Goniometer will be used to assess cervical range of motion (CROM) and joint position sense as shown in figure1.

[figure not shown]

Fig. 1: Standard goniometer

B. Treatment tools:

Extracorporeal shockwave therapy (GymnaUniphy NV [name] Radial extracorporeal shockwave therapy) (rESWT) pneumatic type machine (figure2).

Fig. 2: Extracorporeal shock wave therapy.

A. Assessment procedures:

Assessment will be done at base line and after 4 weeks of treatment.

Pressure Pain Threshold

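### As planned, the trial gives no estimate of the effect on patient-reported pain intensity, although pain is the first outcome in its question and purpose

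*Combined protocol and SAP*

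**What the plan says.** The Statement of the problem asks about the effect of adding shockwave therapy to "Routine physiotherapy on pain, function, range of motion (ROM), and position sense in patients with chronic mechanical neck pain". The Purposes of the study section repeats the list, again with pain first: "Routine physiotherapy on neck pain, function, ROM, joint position sense in patients with chronic mechanical neck pain".

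The methods use a pain-intensity score once, in Chapter III, Inclusion criteria, item 4: "Patient visual analogue scale (VAS) 3 to 8 out of 10".

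The outcome instruments form a closed list. Delimitations, item 3 begins "The instrumentations will be limited to: Pressure algometer to assess pressure pain threshold" and then adds only the Arabic NDI for function and a goniometer for range of motion and joint position sense. The Assessment tools in Chapter III are the same three. On timing, the plan states: "Assessment will be done at base line and after 4 weeks of treatment".

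The hypothesis closest to pain is the first: "There will be no significant effect of adding ESWT to routine physiotherapy on pressure pain threshold in patients with MNP". The other 13 concern neck function (one), active range of motion (six) and joint position sense (six).

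**The concern.** PPT and pain intensity are different quantities. As described under Pressure Pain Threshold, PPT is the pressure on a taut band of the upper trapezius at which the patient says pressure has become pain. It measures evoked tenderness in one muscle, the same muscle to which shockwave is applied. It does not record how much neck pain the patient has. Either could change without the other.

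The plan's own literature review keeps the two apart. The shockwave section of Chapter II lists pain intensity and PPT as separate outcomes of earlier work and cites one comparison in which pain was scored by VAS. The Assessment of MNP section pairs the NDI with a numeric pain-rating scale for neck pain and disability and introduces the algometer separately. The methods adopt no pain-rating scale as an outcome.

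The first-named outcome therefore has no direct measure. A gain in PPT would invite a conclusion about neck pain that no pain score supports. A change in pain intensity without a matching change in PPT could be seen only indirectly, through the NDI. A week-4 score that was never taken cannot be recovered later.

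**Working it through.** **1. Aims against measurements.**

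| Outcome in the research question | Instrument at baseline and week 4 | Hypotheses |
|---|---|---|
| Pain | Algometer (PPT); no pain-intensity scale | 1, on PPT |
| Function | Arabic NDI | 1 |
| Range of motion | Goniometer | 6 |
| Position sense | Goniometer | 6 |

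The hypotheses sum to 1 + 1 + 6 + 6 = 14. Stand-alone pain-intensity measurements planned after baseline: 0. Hypotheses on pain intensity: 0 of 14.

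**2. How much pain intensity the NDI carries.** The Assessment tools section says the NDI includes a question on pain severity. The Neck disability assessment section gives 10 items, each scored from 0 to 5.
- Maximum total: 10 × 5 = 50.
- Maximum from the pain question: 5, so 5/50 = 10% of the total.

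This is a share of the maximum score, not a measure of how strongly the total responds to a change in pain. The severity bands and the 10% importance threshold refer to the overall score, and no item-level analysis is planned.

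**3. The plan's sample size.** Inputs from Sample size calculation: two-sided alpha 0.05, power 80%, standardised effect 0.8, 1:1 allocation. A two-sample t-test with the noncentral t distribution gives 25.52 per arm, rounded up to 26, so 52 in total. This matches the plan. Power at 26 per arm is 80.7%. The plan does not say which outcome the 0.8 belongs to.

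**4. What 26 per arm would give for a VAS outcome** (unadjusted comparison, no dropout).
- 95% CI half-width = t(0.975, 50) × √(2/26) × SD = 2.0086 × 0.2774 × SD = 0.557 SD.
- Smallest difference detectable with 80% power = 0.792 SD.

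The documents give no VAS SD, so the range below is an assumption.

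| Assumed VAS SD (points) | CI half-width (points) | Detectable difference (points) |
|---|---|---|
| 1.5 | 0.84 | 1.19 |
| 2.0 | 1.11 | 1.58 |
| 2.5 | 1.39 | 1.98 |

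Power is 80.7% at 0.8 SD and 42.4% at 0.5 SD.

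**The case against.** The strongest reply is that the plan does measure pain, in the form it chose. PPT has its own hypothesis, a full procedure at both assessments and a stated minimal clinically important difference of 0.94 kg/cm². The NDI pain-severity question is also answered at both times. The instrument list is explicitly limited, and every hypothesis fits an instrument on it. On this reading the only fault is a broad word in the question and purpose, and narrowing that word would be enough.

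Much of this stands. A reader might infer that the trial cannot estimate any effect on pain. The documents do not support that: PPT gives an estimate for mechanical pain sensitivity, and the NDI item would allow a crude comparison, although none is planned. Narrowing the aim is also a legitimate remedy.

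A reader might also infer that a baseline VAS is collected and then thrown away. That is not supported either. The VAS is an eligibility threshold applied at screening. Nothing says that the score is kept as baseline data, or how close to the baseline assessment it is taken.

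Two further points are fair. The documents give no important difference for VAS, so whether a half-width of 0.8 to 1.4 points is precise enough cannot be settled from them. And no sham is described for group A, so a self-reported pain score would be open to expectation effects. The NDI is self-reported too, and PPT depends on the patient saying when pressure becomes pain, so this is not a particular reason to leave VAS out.

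The reply does not remove the mismatch. The question and purpose say pain, the literature review treats pain intensity and PPT as separate outcomes, and only the second is planned.

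**Conclusion.** The concern holds in this form: the plan provides no estimate of the effect on patient-reported pain intensity, although pain is the first outcome in its question and purpose. VAS is used only for eligibility. After baseline, pain is represented by PPT at the upper trapezius and by one NDI question worth at most 10% of the maximum score.

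No figure in the plan is wrong on this point, and the sample size of 52 reproduces. It would be too strong to say that results will be misreported, since the first hypothesis is worded correctly as PPT. It would also be too strong to say that any pain relief would go unseen, since some could show in the NDI.

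The existing sample would serve a VAS outcome at the effect size already assumed (0.8 SD, about 80% power) but not a moderate one (0.5 SD, about 42%). These figures assume no dropout and no gain from baseline adjustment. The conversion to points rests on an assumed SD of 1.5 to 2.5. The gap is worth closing because the remedy is cheap.

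**What to change.** 1. Record the same 0-10 VAS at the baseline assessment and at week 4. If the entry score is taken at the baseline visit, record it formally as the baseline value instead of asking twice.
2. Add VAS to the instrument list in Delimitations and Assessment tools, and add a hypothesis naming it as the pain-intensity outcome.
3. Compare week-4 VAS between arms, adjusted for baseline VAS, and report the difference with its 95% confidence interval.
4. Describe PPT throughout as pressure pain sensitivity.
5. If VAS is not added, restate the question and purpose as an effect on PPT rather than on pain.

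The cost is one self-report question at two assessments that already take place, and one baseline-adjusted model beside the planned repeated-measures MANOVA. There is one more outcome to place in whatever multiplicity order is adopted. The lack of a described sham should be stated as a limitation of VAS, as it should be for the NDI and PPT. The sample size need not change for an effect of 0.8 SD. If a smaller effect on pain matters, the limited power should be stated in advance.

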Extracorporeal shock wave therapy on myofascial condition is now the subject of more research to determine its effectiveness, especially in the upper trapezius which need further research to confirm its pain-relieving characteristics and their capability to promote tissue proliferation and repair (**Rahbar., 2021**). ESWT combined with Wuqinxi exercise can relieve pain, increase joint range of motion and muscle strength better than conventional ultrasound therapy (**Lin S et al.,2023**). extracorporeal shock wave therapy is superior to other treatments in terms of alleviating the pain intensity and pressure pain threshold of patients with myofascial pain syndrome in the neck and shoulder (**Jun, J.H et al.,2021**). ESWT can avoid the adverse effects of invasive procedures on patient; compared with TPI, dry needling and US, ESWT can more effectively relieve the pain of MPS patients (**Tao wu et al., 2022**). Both dry needle and ESWT applications may improve pain level (based on VAS) and ROMs in patients with active trigger points in upper trapezius muscle (**Toghtamesh et al.,2020**).

CHAPTER III

PATIENTS, MATERIALS, AND METHODS

The aim of this study is to examine the effect of adding ESWT to conventional physiotherapy program in treatment of chronic mechanical neck pain. It will be conducted at the outpatient clinic of physiotherapy, faculty of physical therapy, Benha University from July 2023 to Jun 2024.

Study design

This study will be Double-blinded (participant, statistician and evaluator), pretest- posttest controlled trial.

Patients

Fifty-two patients with mechanical neck pain screened by the principal researcher will be included for study after being informed about study aim and signing the consent form (APPENDIX I).

The study subjects will be randomly assigned into two groups A and group B (ratio 1:1) using a computer-generated random data sheet using www. random. Org.

Group A will receive only routine physiotherapy in the form of stretching, isometric training, and home program of postural correction. Group B will receive ESWT combined with routine physiotherapy. The treatment will last 4 weeks, 2 sessions weekly one session with ESWT and another without.

Sample size calculation

Sample size calculation was done using G-POWER 3.1 software and considering two-sided $\alpha = 0.05$, power = 80% and Effect size = 0.8 (large) based on the study of **Cho et al. (2012)**, the total sample size was calculated to be 52 (26 in each group).

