For the purpose of measuring the local pressure pain threshold in the upper trapezius, a pressure algometer (Baseline algometer 10kg) will be used. The person will lie down in a prone lying position. After identifying a taut band, a digital pressure algometer will be used to apply pressure perpendicular to the muscle fibers at a rate of 4 to 5 N/s (40–50 kPa/s). Patients will be instructed to provide the examiner with the specific instant at which pressure changed into pain. After that, the test will be repeated three times, with a minimum 30-second gap between each test, and the average will be calculated and the whole procedures will be repeated on the opposite side (**Blanpied et al., 2017; Jun et al., 2021**). Searching for taut bands in trapezius based on anatomically predicted sites of taut bands: MTrP1

intermediate part of the anterior border of the upper part of the muscle near the vertical fibers of the muscle attached to clavicle. MTrP2 distal and slightly lateral to MTrP1. MTrP3 medial to the scapula and on the border of the medial fibers near the inferior border of the muscle. MTrP3.1 medial fibers near the inferior margin of the muscle, medial to MTrP3; nervous branch. MTrP5 medial to scapula in the intermediate part of muscle belly. MTrP5.1 medial to the scapula in the intermediate part of the muscle belly inferior to MTrP5.1. MTrP5.2 medial to the scapula in the intermediate part of the muscle belly. inferior to MTrP5.1 (**Akamatsu et al., 2015**). The previous muscle's taut bands will be evaluated: upper fibers of the trapezius. A mean difference of 0.94 kg/cm^2 in pain pressure threshold was considered as minimal clinically important difference (**Asiri et al., 2020**).

Neck disability assessment

A 10-item neck disability index (NDI) will be used to assess neck disability. Each item will be evaluated and scored on a 5-point scale, with 0 denoting "no handicap" and 5 denoting "full disability." According to the final score, mild, moderate, and severe disabilities were respectively, 5, 14, 15, 24, and 25 (**Vernon and Mior, 1991**). The Arabic version of NDI is reliable (**Elbeltagy et al., 2018**). In the current investigation, a 10% reduction in the neck disability score was considered to be the lowest clinically significant difference (**Lauche et al., 2013**).

Cervical range of motion assessment

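### The pressure pain threshold (PPT) test point is found by palpation and is not fixed between baseline and week 4, and no rule says how the two sides give one value for Hypothesis 1

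*Combined protocol and SAP*

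**What the plan says.** The assessment procedures are run twice, at baseline and at the end of the four treatment weeks. For PPT there is one written procedure, in the Pressure Pain Threshold section: "After identifying a taut band, a digital pressure algometer will be used to apply pressure perpendicular to the muscle fibers". That section lists seven labelled trapezius sites where bands may be sought and then limits the evaluation to the upper fibers. The reading is repeated three times and averaged, and then "the whole procedures will be repeated on the opposite side".

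Four other places bear on this:

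- Inclusion criterion 3 asks only this of the patient: "Patient has at least one taut band at upper fibers of trapezius". A band on each side is not required.
- Significance of the study, discussing myofascial syndrome as a source of pain, says "hence breaking the cycle of pain by relaxing tense bands is primary goal of its treatment".
- Hypothesis 1 is one statement with no side named: "There will be no significant effect of adding ESWT to routine physiotherapy on pressure pain threshold". For range of motion and joint position sense, by contrast, side bending and rotation have separate right and left hypotheses.
- The Statistical analysis section plans a repeated-measures MANOVA on the pre and post values. It does not mention the two PPT sides or a PPT reading that could not be taken.

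The documents do not say which band is tested if there are several, whether the baseline point is marked and reused, or what the evaluator does if no band is palpable at week 4.

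**The concern.** A change score means something only if the same thing is measured twice. Here the location of the measurement is defined by a physical sign that the treatment is meant to remove. An evaluator who follows the text at week 4 starts by looking for a taut band. If the baseline band has resolved, the evaluator must test a different site, press on muscle without a band, or take no reading. Which patients this affects depends on how they responded. If bands resolve more often in one arm, the choice of site differs by arm, and neither randomisation nor a blinded evaluator removes that difference.

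The second side raises a separate problem. Each patient may have two PPT values at each visit, while Hypothesis 1 needs one comparison. Averaging the sides, choosing one, or analysing right and left separately all remain open until the data are in. These options do not answer the same question or have the same power.

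**Working it through.** **1. The plan's own figure.** Inputs from Sample size calculation: two-sided alpha 0.05, "power = 80% and Effect size = 0.8 (large) based on the study of" a cited earlier study, and 26 per group. A two-sample t-test (noncentral t) with d = 0.8 needs 25.52 per group, which rounds up to 26 per group and 52 in total. Power at 26 per group is 80.7%. The stated figure reproduces and is not in dispute. The section does not say which outcome the 0.8 refers to, so using it for PPT is an assumption.

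**2. The test point.** The relevant statements, side by side:

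- The procedure begins by identifying a band.
- The same procedure applies at both visits.
- No sentence fixes, records or returns to the baseline point.
- Relaxing bands is a stated goal of treatment.

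So a different point is permitted at week 4, and whether it is needed can depend on response. The possible consequences do not share a direction:

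- A substitute band that is still tender would lower the week-4 reading in a responder.
- A substitute trapezius site that was also treated, or muscle now free of a band, could read the same or higher.
- No reading gives a missing value related to response, with an unknown effect.

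Bands can also resolve in the control arm, because both arms stretch the upper trapezius. The documents give no resolution rates, so no figure can be attached to this part.

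**3. The two sides, if averaged.** Let f be the mean opposite-side effect as a fraction of the index-side effect, and rho the between-side correlation, with equal SD on both sides. Then

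d' = 0.8 × [(1 + f)/2] / √[(1 + rho)/2].

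For example, f = 0 and rho = 0.5 give 0.8 × 0.5 / √0.75 = 0.40/0.866 = 0.46. With f = 1 and rho = 0.5, d' = 0.80/0.866 = 0.92. Power at 26 per group:

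| f | rho 0.5 | rho 0.7 | rho 0.9 |
|---|---|---|---|
| 0 | d' 0.46, 37% | d' 0.43, 34% | d' 0.41, 31% |
| 0.5 | d' 0.69, 69% | d' 0.65, 63% | d' 0.62, 59% |
| 1 | d' 0.92, 90% | d' 0.87, 87% | d' 0.82, 83% |

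For 80% power with f = 0, 75, 85 or 95 per group would be needed.

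Averaging beats a single index side only when (1 + f)/2 exceeds √[(1 + rho)/2], that is, f > 2√[(1 + rho)/2] − 1. This is f > 2 × 0.866 − 1 = 0.73 at rho = 0.5, and f > 2 × 0.975 − 1 = 0.95 at rho = 0.9. Neither f nor rho is in the documents. The PPT minimal clinically important difference of 0.94 kg/cm² comes without an SD, so it cannot be turned into a standardized effect either.

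**The case against.** The strongest reply is that the text is silent rather than wrong. It does not order a new search at week 4 or forbid returning to the baseline site, and it confines testing to the upper trapezius. That is fair, and a careful evaluator might retest the same point. But the only written procedure starts with finding a band, so following it literally allows the point to move. The statement about relaxing bands concerns myofascial syndrome in general rather than ESWT in particular, but it still makes band presence something treatment is expected to change.

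A reader might infer that the distortion must pull the ESWT effect toward zero. The documents do not support that. It assumes that resolved bands are replaced by tender, unimproved ones, mainly in the ESWT arm, and none of this is stated.

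A reader might also infer that the opposite side does dilute the effect. That needs both pooling of the sides and a weaker response on the opposite side. The only average described is over the three repeats, and ESWT is directed at trapezius trigger points with no limit to one side. If both sides respond equally, averaging raises power above 80.7%.

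Nor do the documents support a claim that sides will be entered as independent observations, with an inflated type I error. The sample is counted in patients, and a MANOVA can carry right and left PPT as separate variables for each patient. That reading neither pools nor double-counts. It would, however, leave Hypothesis 1 with two answers. In patients with a band on one side only, it would also mix affected and unaffected sides within each variable.

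**Conclusion.** The point stands as a gap in the definition of the endpoint. As written, the PPT site is tied to a sign that treatment may remove, so the baseline and week-4 readings may not refer to the same spot, and the mismatch can differ between arms. Its direction and size are unknown. Separately, the single PPT value for Hypothesis 1 is undefined when two sides are measured.

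The 31-37% to 83-90% power range applies only if the sides are averaged. It rests on an assumed index-side d of 0.8, equal SDs and an assumed rho of 0.9 to 0.5. It shows how much depends on the unwritten rule and does not predict where this trial falls. The sample size of 52 is unaffected. If 0.8 is the index-side effect, analysing one fixed index point keeps power at 80.7%. The change is worth making because it is nearly free.

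**What to change.** Add to the Pressure Pain Threshold section that at baseline the tested point and its side are recorded by measured distance from fixed landmarks, and that exactly this point is retested at week 4 whether or not a band is still palpable. State how the baseline point is chosen when there are several bands.

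In the Statistical analysis section, pre-specify before unblinding one PPT value per patient for Hypothesis 1. One option is the baseline index point, with the opposite side reported separately. Another combination is acceptable if it is written down in advance, including what happens when the opposite side has no band.

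The cost is about one protocol sentence for the measurement, a short analysis rule and two extra fields on the assessment form. No equipment, staff or visits are added. If the site with the lowest baseline PPT is chosen as the index, regression to the mean will raise the week-4 readings. It is expected to do so equally in both arms, so the between-arm comparison is not biased, but within-arm changes should not be read as treatment effects. Reporting the opposite side only descriptively gives up some information if both sides respond.
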